5.2.7. Definition of on-treatment period

Safety endpoints will be summarized based on the on-treatment period unless otherwise specified.

On-treatment period is defined as the time from the first dose of study treatment through minimum (28 days + last dose of study treatment, start day of new anti-cancer drug therapy – 1 day).

Safety data collected outside the on-treatment period as described above will be listed and flagged in listings but not summarized.

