3.4. Baseline Variables

In this study, 'study drug' refers to PF-07901801 or tafasitamab or lenalidomide, and 'study treatment' refers to PF-07901801 plus tafasitamab plus lenalidomide.

Start and end dates of study treatment:

The date of first dose of study treatment is the earliest date of the first non-zero dose date for the study drugs in the combination.

The date of last dose of study treatment is the latest date of the last non-zero dose date for the study drugs in the combination.

Definition of baseline:

Definition of baseline for efficacy analyses

The last measurement prior to or on the 'start date' will serve as the baseline measurement for efficacy analyses. For Phase 2 patients, if such a value is missing, the last measurement prior to the first dose of study treatment will be used as the baseline measurement except for analyses of tumor data where the baseline assessment would be considered as missing.

Definition of baseline for safety analyses

The last available assessment prior to the start of study treatment is defined as 'baseline' value or 'baseline' assessment for safety analyses. If an assessment is planned to be performed prior to the first dose of study treatment in the protocol and the assessment is performed on the same day as the first dose of study treatment, it will be assumed that it was performed prior to study treatment administration, if assessment time point is not collected or is missing. If assessment time points are collected, the observed time point will be used to determine pre-dose on study day 1 for baseline calculation. Unscheduled assessments will be used in the determination of baseline. However, if time is missing, an unscheduled assessment on study day 1 will be considered to have been obtained after study treatment administration.

Patients who start treatment and discontinue from the treatment/study on the same day may have two different sets of data collected on study day 1 (one during study and one in the End of Treatment (EOT) visit. Data reported at the EOT visit are not eligible for baseline selection.

If a scheduled pre-dose measurement actually occurred post-dose, then the corresponding measurement will be treated and analyzed similar to an unscheduled post-dose measurement.

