3.5. Safety Endpoints

3.5.1. Adverse Events

Treatment-Emergent Adverse Events

Treatment-emergent adverse events (TEAEs) are those events with onset dates occurring during the on-treatment period, or if the worsening of an event is during the on-treatment period.

On-treatment period is defined as the time from the first dose of study treatment through minimum (28 days + last dose of study treatment, start day of new anti-cancer drug therapy – 1 day). The start day of new anti-cancer drug therapy after the first dose of study treatment is derived as outlined in Section [5.2.5](#).

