5.2.5. Definition of start of new anti-cancer drug therapy

Start date of new anti-cancer drug therapy is used to determine the end of the on-treatment period (see Section [5.2.7](#)).

The start date of new anti-cancer drug therapy is the earliest start date of anti-cancer drug therapy recorded in the 'Follow-up Cancer Therapy' eCRF pages that is after the first dose of study treatment. When start date of anti-cancer drug therapy is missing or partially missing, the imputation rules described in Section [5.3.3.4](#) should be applied using only data from the 'Follow-up Cancer Therapy' eCRF pages.

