5.2.6. Definition of start of new anti-cancer therapy

Start date of new anti-cancer therapy (drug, radiation, surgery) is used for censoring in efficacy analyses.

The start date of new anti-cancer therapy is the earliest date after the first dose of study treatment amongst the following:

- Start date of anti-cancer drug therapy recorded in the 'Follow-up Cancer Therapy' eCRF pages
- Start date of radiation therapy recorded in 'Radiation' eCRF page with 'Treatment Setting' = 'Curative'
- Surgery date recorded in 'Cancer Surgery' eCRF page when 'Surgery Outcome' = 'Resected' or 'Partially Resected'.

When start date of anti-cancer therapy is missing or partially missing, the imputation rules described in Section 5.3.3.4 should be applied using 'Follow-up Cancer Therapy', 'Radiation', and 'Cancer Surgery' eCRF pages.

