6.7. Safety Summaries and Analyses

Summaries of AEs and other safety parameters will be based on the Safety Analysis Set.

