6.7.1. Adverse Events

Treatment-emergent adverse events (TEAEs) are those events with onset dates occurring during the on-treatment period for the first time, or if the worsening of an event is during the on-treatment period as defined in Section 5.2.7.

All analyses described below will be based on TEAEs if not otherwise specified. The AE listings will include all AEs (whether treatment-emergent or not). AEs outside the on-treatment period will be flagged in the listings. Summaries of TEAEs due to COVID-19 may be produced if appropriate.

- Related Adverse Events: adverse events with relationship to study treatment (as recorded on the AE eCRF page, Relationship with study treatment = Related) reported by the investigator and those of unknown relationship (i.e., no answer to the question 'Relationship with study treatment'). Related AEs are those related to any study drug (ie, at least one of the study drugs).
- Serious Adverse Events (SAE): serious adverse events (as recorded on the AE eCRF page, Serious Adverse Event = Yes).
- Adverse Events Leading to Dose Reduction: adverse events leading to dose reduction of study treatment (as recorded on the AE eCRF page, Action taken with study treatment = Dose reduced).

- Adverse Events Leading to Interruption of Study Treatment: adverse events leading to interruption of study treatment (as recorded on the AE eCRF page, Action taken with study treatment = Drug interrupted).
- Adverse Events Leading to Permanent Treatment Discontinuation: adverse events leading to permanent discontinuation of study treatment (as recorded on the AE eCRF page, Action taken with study treatment = Drug withdrawn).
- Adverse Events Leading to Death: adverse event leading to death (as recorded on the AE eCRF page, Outcome = Fatal, as well as AEs of Grade 5).

Unless otherwise specified, AEs will be summarized by number and percentage of patients with the AE in the category of interest as described above, by treatment group, primary SOC and PT.

Each patient will be counted only once within each SOC or PT. If a patient experiences more than one AE within a SOC or PT for the same summary period, only the AE with the strongest relationship or the worst severity, as appropriate, will be included in the summaries of relationship and severity.

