6.7.3. Serious Adverse Events

The frequency (number and percentage) of patients with each of the following will be presented for treatment-emergent SAEs by treatment group:

- SAEs by SOC and PT
- Related SAEs by SOC and PT

The listings of all SAEs will also be provided with the relevant information with a flag for SAEs with onset outside of the on-treatment period.

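### SAP AE and SAE tables stop 28 days after the last dose or at new drug therapy, while the protocol collects to 90 days after tafasitamab; the narrowing is not declared in SAP 2.1

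*SAP*

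**What the plan says.** **The SAP window.** SAP 3.5.1 reads: "On-treatment period is defined as the time from the first dose of study treatment through minimum (28 days + last dose of study treatment". The other term of that minimum is the day before new anticancer drug therapy. SAP 5.2.7 repeats the rule and adds: "Safety data collected outside the on-treatment period as described above will be listed and flagged in listings but not summarized". Under SAP 3.4 the last dose of study treatment is "the latest date of the last non-zero dose date for the study drugs in the combination", so any of the three drugs can set it.

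**The tables.** SAP 6.7 names the population: "Summaries of AEs and other safety parameters will be based on the Safety Analysis Set". SAP 6.7.1 fixes the period: "All analyses described below will be based on TEAEs if not otherwise specified". The SAE frequencies in SAP 6.7.3 "will be presented for treatment-emergent SAEs by treatment group". SAP 6.7.2 is wider and tabulates deaths at any time.

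**The protocol.**
- Section 8.4.1 runs active collection from consent to at least 28 days after PF-07901801 and/or lenalidomide or 90 days after tafasitamab, taking the longer.
- Section 8.1.2 schedules a 90-day follow-up contact that covers AEs.
- Section 8.4.1.2 stops non-serious AE recording when a new anticancer therapy starts, but continues SAE recording to the end of the collection period.
- Section 9.4.3.2.1 says the AE summaries span the whole of the study and attaches no on-treatment limit.
- Section 9 allows the SAP to modify the outlined analyses.

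SAP 2.1, where modifications of the protocol's analysis plan are recorded, says only that none apply.

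**The concern.** The overall safety profile is a Phase 1b secondary objective. Phase 2 will not start, so the Phase 1b tables will be this study's safety results.

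Take a non-fatal SAE on day 40 after the last tafasitamab dose, with no later dose of another drug. The site must record and report it. Under the SAP it appears in a listing and in no count or percentage by dose level. The tables affected are the overall AE summary, the six SOC/PT tables in SAP 6.7.1.1 and the two SAE tables in SAP 6.7.3. On the natural reading of protocol 9.4.3.2.1 the event should be summarized. Neither document explains the difference.

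The version gap does not appear to explain it. SAP version 2 follows protocol Amendment 1, and neither amendment's change table lists a change to protocol 8.4.1 or 9.4.3.2, apart from general editorial entries.

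**Working it through.** The plan states no figure to reproduce, so the check is date arithmetic on its own rules.

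**Inputs.** Let L be the days from the last tafasitamab dose to the last dose of any study drug. Day counts below run from the last tafasitamab dose.
- SAP end without new therapy (SAP 3.4, 3.5.1, 5.2.7): L + 28.
- Protocol collection end (8.4.1): the larger of 90 and L + 28.
- Collected but not tabulated: max(0, 62 − L) days.

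**Values of L on the scheduled days (protocol 6.1.1.1 to 6.1.1.3).** In Cycles 1 to 3 tafasitamab is last given on Day 22 and lenalidomide on Day 21, so L = 0. In Cycles 4 to 12 tafasitamab is last given on Day 15 and lenalidomide on Day 21, so L = 6. After Cycle 12 lenalidomide has stopped, so L = 0.

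**Tail by treatment length**, with study day 1 = C1D1, full cycles and no new therapy:

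| Cycles | Last tafasitamab | Last dose of any drug | SAP end | Collection end | Tail | Share |
|---|---|---|---|---|---|---|
| 1 | 22 | 22 | 50 | 112 | 62 | 62/112 = 55% |
| 3 | 78 | 78 | 106 | 168 | 62 | 62/168 = 37% |
| 6 | 155 | 161 | 189 | 245 | 56 | 56/245 = 23% |
| 12 | 323 | 329 | 357 | 413 | 56 | 56/413 = 14% |

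The tail shrinks when tafasitamab stops first: 34 days at L = 28, 6 days at L = 56, and 0 from L = 62.

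**New anticancer drug on day s after the last dose, with L = 0.**
- For s ≤ 28 the tables stop at day s − 1. The SAE tail is 90 − (s − 1) = 91 − s days: 90 for s = 1, 76 for s = 15 and 63 for s = 28. The non-serious tail is 0, because recording also stops at the new therapy.
- For s from 29 to 90 the SAE tail stays at 62 days and the non-serious tail is s − 29 days, from 0 to 61.

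**Step size, for illustration only.** Assume the planned 20 participants split equally over the three planned dose levels, giving 20/3 = 6.7 per level. One participant whose only SAE is late then moves that level's SAE percentage by 100/6.67 = 15 points. The step is 20 points with 5 participants and 10 points with 10.

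**The case against.** The strongest reply is that the conflict rests on an undefined phrase. Protocol 9.4.3.2.2 uses the same whole-study wording for laboratory data in a paragraph that also restricts them to the on-treatment period. The authors may have meant all cycles rather than the DLT period alone. This stands as far as it goes: the wording is ambiguous and both places need clarifying. But the AE paragraph carries no on-treatment limit, so its natural reading still differs from the SAP.

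The SAP may also narrow the analysis. Protocol section 9 permits it, a longer collection period does not oblige tabulation over the same period, and the SAP states its window openly. That makes a 28-day main analysis legitimate. It does not account for SAP 2.1 declaring no modification, or for the absence of any summary of later SAEs.

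The practical effect may be small. The study is terminated, the dataset is small and descriptive, and late events remain in flagged listings. The percentages above assume survival through the collection period and no new therapy, although PF-07901801 and tafasitamab are normally given until progression, intolerable toxicity or death. The 15-point step is simply one over the group size. All of this is fair and limits the severity. It still leaves non-fatal late SAEs without counts by dose level.

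Finally, protocol 8.4.1.2 stops non-serious recording at new anticancer therapy, which may include radiation or surgery, whereas SAP 5.2.5 concerns drugs only. Events that are not recorded are counted under neither date, and the main tables already use the drug date, so this does not count against the remedy below.

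**Conclusion.** The concern holds and should be fixed. The SAP limits its AE and SAE tables to a shorter period than the protocol collects and, on its natural reading, intends to summarize. It does not record that restriction as a modification.

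On scheduled dosing with no new therapy the omitted tail is 62 or 56 days. It falls to 0 if tafasitamab stopped at least 62 days before the last dose of another drug. For SAEs with L = 0 it rises to between 63 and 90 days when a new anticancer drug starts within 28 days of the last dose.

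These figures rest on the scheduled dosing days and on follow-up to the end of collection. The documents do not give the frequency of late events, so no effect on the safety conclusions can be estimated. The DLT endpoint and the death table are unaffected.

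**What to change.** Keep the 28-day TEAE tables as the main analysis and make these additions:

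1. In SAP 5.2.7, define a supplementary AE reporting period from first dose to the end of the protocol 8.4.1 collection period. Count SAEs throughout. Count non-serious AEs to the day before new anticancer drug therapy as defined in SAP 5.2.5.
2. On that period, add three summaries by SOC and PT: any AE, Grade 3 or higher AE, and SAE. A fatal-AE table is optional, given SAP 6.7.2. Pre-dose AEs stay in the listings.
3. Record the 28-day restriction of the main tables in SAP 2.1.
4. Reconcile the whole-study wording in protocol 9.4.3.2.1 and 9.4.3.2.2 with SAP 6.7.1 and 6.7.4.

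SAP 5.2.5 is the right trigger because it already closes the main window: "Start date of new anti-cancer drug therapy is used to determine the end of the on-treatment period". SAP 5.2.6 serves another purpose: "Start date of new anti-cancer therapy (drug, radiation, surgery) is used for censoring in efficacy analyses". Under 5.2.6, curative radiation on day 10 after the last dose would stop the supplementary non-serious count at day 9 while the TEAE count ran to day 28. The supplementary table could then hold fewer events than the main one.

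The cost is one date derivation (with separate ends for serious and non-serious events), three tables, one SAP 2.1 entry and a wording clarification, all from data already collected. The drawback is that some late events will reflect the disease or subsequent therapy, and the added tables will not separate them.

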5.2.8. Standard derivations and reporting conventions

The following conversion factors will be used to convert days into weeks, months or years: 1 week = 7 days, 1 month = 30.4375 days, 1 year = 365.25 days.

Demographics and physical measurements:

- Age [years]: (year of given informed consent - year of birth)
- Body mass index (BMI) (kg/m^2) = weight (kg)/[height (m)]²

For reporting conventions, mean and median should generally be displayed one more decimal place than the raw data and standard deviation should be displayed to two more decimal places than the raw data. Percentages will be reported to one decimal place. The

rounding will be performed to closest integer / first decimal using the common mid-point between the two consecutive values. E.g., 5.1 to 5.4 will be rounded to an integer of 5, and 5.5 to 5.9 will be rounded to an integer of 6.

5.2.9. Unscheduled Visits

Generally, data collected at unscheduled visits will be included and analyzed for both safety and efficacy analyses in the same fashion as the data collected at scheduled visits except where otherwise noted in the sections that follow. Descriptive statistics (mean, SD, median, minimum, maximum, quartiles) by nominal visit or time point for safety endpoints such as laboratory measurements, ECGs and vital signs will include only data from scheduled visits.

5.2.10. Adequate Baseline Disease Assessment

Adequate baseline is defined using the following criteria:

- All baseline assessments must be within 42 days prior to and including the 'start date'.
- Baseline lesions must be assessed with an acceptable method of tumor assessment as specified in the protocol and must include PET/CT, or PET and CT, or possibly PET /MRI or PET and MRI in some circumstances.
- At least 1 target, PET-avid lesion must be identified.
- All lesions (target and non-target) must have non-missing assessments. For target lesions, non-missing measurements and the longest diameter should meet the criteria for being measurable; for non-target lesions, non-missing lesions status at baseline.

5.2.11. Adequate Post-baseline Disease Assessment

An adequate post-baseline assessment is defined as an assessment where a response of CR, PR, SD, or PD can be determined. Time points where the response is not evaluable (NE) or no assessment was performed will not be used for determining the censoring date for time-to-event endpoints including PFS, DoR, and DoCR.

5.2.12. Analyses for Continuous and Qualitative Variables

Continuous variables will be summarized using descriptive statistics ie, number of nonmissing values and number of missing values [ie, n (missing)], mean, median, standard deviation, minimum, maximum and first and third quartile (Q1 and Q3).

Qualitative variables will be summarized by frequency counts and percentages. Unless otherwise specified, the calculation of proportions will include the missing category. Therefore, counts of missing observations will be included in the denominator and presented as a separate category.

In case the analysis refers only to certain visits, percentages will be based on the number of participants still present in the study at that visit, unless otherwise specified.

5.2.13. Analyses for Time-to-Event Endpoints

Kaplan-Meier estimates (product-limit estimates) will be presented together with a summary of associated statistics including the median time with 2-sided 95% CIs. Probabilities of an event at particular timepoints will be estimated with corresponding 2-sided 95% CIs. The CI for the median will be calculated according to Brookmeyer and Crowley, 1982^[3] and the CIs for the survival function estimates at particular timepoints will be derived using the log(-log) method^[4].

5.3. Methods to Manage Missing Data

Unless otherwise specified, all data will be evaluated as observed, and no imputation method for missing values will be used.

In all patient data listings imputed values will be presented. In all listings imputed information will be flagged.

Missing statistics, e.g. when they cannot be calculated, should be presented as 'ND' or 'NA'. For example, if N=1, the measure of variability (SD) cannot be computed and should be presented as 'ND' or 'NA'.

5.3.1. Missing Pharmacokinetic Data

5.3.1.1. Pharmacokinetic Concentrations

Concentrations below the limit of quantification

For all calculations, tables and figures, all concentrations assayed as below the level of quantification (BLQ) will be set to zero. The BLQ values will be excluded from calculations of geometric means and their CIs. A statement similar to 'All values reported as BLQ have been replaced with zero' should be included as a footnote to the appropriate tables and figures.

Deviations, missing concentrations and anomalous values

In summary tables and median profiles, concentrations will be set to missing if one of the following cases is true:

1. A concentration has been reported as ND (i.e., not done) or NS (i.e., no sample);
2. A deviation in sampling time is of sufficient concern or a concentration has been flagged as anomalous by the clinical pharmacologist.

At the discretion of the clinical pharmacologist, summary statistics may not be presented at a particular time point if more than 50% of the data are missing. For analysis of pharmacokinetic concentrations, no values will be imputed for missing data.

5.3.1.2. Pharmacokinetic Parameters

If a PK parameter cannot be derived from a patient's concentration data, the parameter will be coded as NC (i.e., not calculated). NC values will not be generated beyond the day that a patient discontinues.

In summary tables, statistics will be calculated by setting NC values to missing. Statistics will not be presented for a particular treatment if more than 50% of the data are NC. For statistical analyses (i.e., analysis of variance), PK parameters coded as NC will also be set to missing.

If an individual patient has a known biased estimate of a PK parameter (due for example to a deviation from the assigned dose level), this will be footnoted in summary tables and will not be included in the calculation of summary statistics or statistical analyses.

5.3.2. Handling of Incomplete or Missing Dates

5.3.2.1. Disease History

Incomplete dates for disease history (e.g., initial diagnosis date, date of documented, locally advanced, metastatic disease diagnosis, date of response or progression on prior treatment) will be imputed as follows:

- If the day is missing, it will be imputed to the 15th day of the month.
- If both day and month are missing and the year is prior to the year of the first study treatment, the month and day will be imputed as July 1st.
- If both day and month are missing and the year is same as the year of the first study treatment, the month and day will be imputed as January 1st.
- If the date is completely missing, no imputation will be performed.

5.3.2.2. Adverse Events

Incomplete AE-related dates will be imputed as follows:

- If the AE onset date is missing completely, then the onset date will be replaced by the start of study treatment.
- If only the day part of the AE onset date is missing, but the month and year are equal to the start of study treatment, then the AE onset date will be replaced by the start of study treatment. For example, if the AE onset date is --/JAN/2015, and study treatment start date is 15/JAN/2015, then the imputed AE onset date will be 15/JAN/2015.
- If both the day and month of the AE onset date are missing but the onset year is equal to the start of study treatment, then the onset date will be replaced by the start of

study treatment. For example, if AE onset date is --/--/2014, and study treatment start date is 19/NOV/2014, then the imputed AE onset date will be 19/NOV/2014.

- In all other cases the missing onset day or missing onset month will be replaced by 1.
- Incomplete stop date will be replaced by the last day of the month (if day is missing only), if not resulting in a date later than the date of patient's death. In the latter case the date of death will be used to impute the incomplete stop date.
- In all other cases the incomplete stop date will not be imputed. If stop date of AE is after date of cut-off outcome of AE is ongoing at cut-off.

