#### **8.4.1. Time Period and Frequency for Collecting AE and SAE Information**

The time period for actively eliciting and collecting AEs and SAEs (“active collection period”) for each participant begins from the time the participant provides informed consent, which is obtained before undergoing any study-related procedure and/or receiving study intervention, through and including a minimum of 28 calendar days after the last administration of PF-07901801 and/or lenalidomide or 90 days after the last administration of tafasitamab, whichever is longer.

Follow-up by the investigator continues throughout and after the active collection period and until the AE or SAE or its sequelae resolve or stabilize at a level acceptable to the investigator.

When a clinically important AE remains ongoing at the end of the active collection period, follow-up by the investigator continues until the AE or SAE or its sequelae resolve or stabilize at a level acceptable to the investigator and Pfizer concurs with that assessment.

For participants who are screen failures, the active collection period ends when screen failure status is determined.

If the participant withdraws from the study and also withdraws consent for the collection of future information, the active collection period ends when consent is withdrawn.

If a participant permanently discontinues or temporarily discontinues study intervention because of an AE or SAE, the AE or SAE must be recorded on the CRF and the SAE reported using the CT SAE Report Form.

Investigators are not obligated to actively seek information on AEs or SAEs after the participant has concluded study participation. However, if the investigator learns of any SAE, including a death, at any time after a participant has completed the study, and they consider the event to be reasonably related to the study intervention, the investigator must promptly report the SAE to Pfizer using the CT SAE Report Form. In addition, if the investigator learns of any second primary malignancy, irrespective of causality or time of diagnosis, the investigator must promptly report the SAE to Pfizer.

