5.3.2.4. Exposure

No imputation will be done for first dose date. Date of last dose of study drug if unknown or partially unknown will be imputed as follows:

- If the last date of study drug is completely missing and there is no End of Treatment eCRF page and no death date, the patient should be considered to be ongoing and use the cut-off date for the analysis as the last dosing date

- If the last date of study drug is completely or partially missing and there is EITHER an End of Treatment eCRF page OR a death date available (within the cut-off date), then imputed last dose date is:
 - = 31DECYYYY, if only Year is available and Year < Year of min (EOT date, death date)
 - = Last day of the month, if both Year and Month are available and Year = Year of min (EOT date, death date) and Month < the month of min (EOT date, death date)
 - = min (EOT date, death date), for all other cases.

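### Two SAP date-imputation rules can contradict a recorded date: AE onset is not checked against a known stop date, and a last-dose month in an earlier year is discarded

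*SAP*

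**What the plan says.** **AE onset (SAP 5.3.2.2).** Three patterns of incomplete onset are set to the first dose date:

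- Nothing known: "If the AE onset date is missing completely, then the onset date will be replaced by the start of study treatment".
- Month and year known: "If only the day part of the AE onset date is missing, but the month and year are equal to the start of study treatment".
- Year known: "If both the day and month of the AE onset date are missing but the onset year is equal to the start of study treatment".

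Any other incomplete onset has its missing day or month set to 1. None of these rules refers to the AE stop date. The section does check an imputed stop date against the date of death, so consistency checks are not foreign to it.

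Under Protocol 8.4.1, active AE collection "begins from the time the participant provides informed consent", so events from screening are in the data. SAP 3.5.1 and 5.2.7 define a TEAE by onset or worsening in the on-treatment period. That period starts at first dose and ends at the earlier of last dose plus 28 days and the day before a new anti-cancer drug.

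**Last dose (SAP 5.3.2.4).** Where an EOT page or a death date exists, there are three branches:

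- Year only, and earlier than the reference year: 31 December of that year.
- "Last day of the month, if both Year and Month are available and Year = Year of min (EOT date, death date"), with the further condition that the month is earlier than the reference month.
- "min (EOT date, death date), for all other cases".

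The reference date is the earlier of EOT and death.

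**The concern.** In the first rule, the recorded stop date can already prove that the event was over before treatment. The imputation ignores it and produces an impossible record (onset after end) that enters the TEAE tables. AEs are a Phase 1b secondary endpoint, and Protocol Amendment 2 leaves Phase 1b as the only part to be reported.

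In the second rule, a known month in an earlier year fits neither specific branch and drops to the catch-all. The result contradicts what the site recorded, and having the month gives a worse answer than having only the year. SAP 5.3.3.4 covers the same situation for new anti-cancer therapy by using the last day of the known month, so this looks like an omitted branch rather than a choice.

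A last-dose date that is too late can affect:

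- duration of exposure;
- lenalidomide relative dose intensity, which divides by duration of exposure (for the two infused drugs, dose intensity uses an intended duration built from cycle start, so it is not affected);
- the end of the on-treatment period;
- the flag for death within 28 days of last dose;
- imputed new-therapy start dates, which use last dose.

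**Working it through.** The rules were applied literally, first to the SAP's own examples and then to test dates. All test dates are illustrative.

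**1. The SAP's examples.** Onset --/JAN/2015 with first dose 15/JAN/2015: "then the imputed AE onset date will be 15/JAN/2015". Onset --/--/2014 with first dose 19/NOV/2014: "then the imputed AE onset date will be 19/NOV/2014". Both reproduce exactly.

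**2. AE onset, first dose 15 Jan 2015.**

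| Recorded onset | Recorded stop | Imputed onset | TEAE? |
|---|---|---|---|
| missing | 10 Jan 2015 | 15 Jan 2015 | yes |
| --/JAN/2015 | 10 Jan 2015 | 15 Jan 2015 | yes |
| --/--/2015 | 10 Jan 2015 | 15 Jan 2015 | yes |
| --/DEC/2014 | 28 Dec 2014 | 1 Dec 2014 | no |
| missing | 20 Feb 2015 | 15 Jan 2015 | yes |

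In the first three rows onset falls 15 − 10 = 5 days after the event ended. The fourth row is classified correctly, and the fifth is a reasonable default. The fault therefore needs both an onset in one of the three patterns and a known stop date before first dose. Capping the imputed onset at the stop date gives 10 Jan 2015 and no TEAE in the first three rows, and changes nothing in the last two.

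**3. Last dose.**

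| Known part | EOT | SAP result | Last day of known month | Difference |
|---|---|---|---|---|
| 2023 | 7 Jan 2024 | 31 Dec 2023 | month not known | none |
| Dec 2023 | 7 Jan 2024 | 7 Jan 2024 | 31 Dec 2023 | 7 days |
| Nov 2023 | 20 Jan 2024 | 20 Jan 2024 | 30 Nov 2023 | 31 + 20 = 51 days |
| Oct 2023 | 20 Jan 2024 | 20 Jan 2024 | 31 Oct 2023 | 30 + 31 + 20 = 81 days |
| Mar 2024 | 7 Apr 2024 | 31 Mar 2024 | 31 Mar 2024 | 0 |

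The first two rows share an EOT date. Adding the month moves the answer out of the recorded year.

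**4. On-schedule EOT.** The Schedule of Activities places EOT at 7 ± 2 days after last treatment, that is 5 to 9 days. To cross a year end, the earliest EOT is 1 January (1 day past 31 December). The latest is 31 December + 9 = 9 January (9 days past). The error past month end is therefore 1 to 9 days. The 51- and 81-day rows need an EOT or death well off that schedule.

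**5. On-treatment window.** In the November example it ends on 20 Jan + 28 days = 17 Feb 2024 instead of 30 Nov + 28 days = 28 Dec 2023. In the December example it ends on 4 Feb instead of 28 Jan 2024. Under SAP 3.4, last dose of study treatment is the latest across the three drugs. These full shifts therefore require that neither other drug was dosed later and that no new anti-cancer drug closed the window first.

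**6. Effect of one record.** Protocol 9.6 targets 2 to 4 participants per cohort. If one participant is wrongly counted for a term, its incidence moves by 1/4 = 25 to 1/2 = 50 percentage points. With 6 to 9 participants at the top dose it moves by 1/9 = 11 to 1/6 = 17 points.

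**The case against.** Setting an unknown onset to first dose is a standard conservative choice in safety reporting. That stands wherever the stop date is missing or falls on or after first dose. A reader might infer that pre-treatment AEs in general become treatment-emergent. The documents do not support that: complete onset dates are left alone, and a partial onset in an earlier month or year keeps its pre-treatment position.

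A reader might also infer that on-treatment windows will run weeks too long. With EOT on schedule they will not, and the conditions in step 5 limit the effect further.

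The triggering data should be scarce. Protocol 6.5 has infusion dates and times recorded in the CRF, and lenalidomide backed by a diary, capsule counts and recorded stop dates. Assuming about 20 participants, evenly spread last-dose dates and a 7-day EOT gap, about 20 × 7/365 = 0.4 would straddle a year end, before asking for a partial date. The count could be higher for lenalidomide, which stops after at most 12 cycles, if a single EOT page covers all drugs; the documents do not say.

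Analyses use cleaned data, and SAP 5.3 flags imputed values in listings, so an affected record would be visible. The tables would still carry the wrong value. What stands is that both rules, as written, give a wrong date in identifiable cases, and no other section corrects them.

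**Conclusion.** Both faults are real and minor. The AE rule errs only for an event with a completely missing onset, or a partial onset matching the first-dose month or year, together with a known stop date before first dose. In that case a recorded fact shows the event was not treatment-emergent, so conservatism does not justify the result. The last-dose rule errs only when month and year are known and the year precedes that of the earlier of EOT and death. The result is then 1 to 9 days past month end with an on-schedule EOT, and more only if EOT or death is late.

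The number of partial dates is not given and is probably very small. The case for acting is that cohorts are small enough for one record to show in a table. A reader might infer a threat to the primary endpoints, but the DLT rate and ORR definitions do not directly use either imputed date.

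**What to change.** 1. **SAP 5.3.2.2.** Keep the existing onset rules and add: if the imputed onset is later than a known AE stop date, set onset to the stop date; make no change if the stop date is missing or the AE is ongoing. Word it as a cap. Taking the earlier of first dose and stop date for every incomplete onset would displace the rule for remaining cases: an onset of --/MAR/2015 with first dose 15 January 2015 would lose its known month.
2. **SAP 5.3.2.4.** Add a branch: if year and month are both available and the year is earlier than the year of the earlier of EOT and death, impute the last day of that month. This mirrors SAP 5.3.3.4.

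The medication start rule in SAP 5.3.2.3 has no stop-date check either and can take the same cap.

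The cost is a few lines of SAP text and derivation code. No data collection changes, and no correctly imputed record is altered.
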